- 16. Patient has received a live vaccination within 8 weeks before Day 1 or inoculation with a live vaccine is planned during study participation.
- 17. Jo-1 Ab levels >7 U/mL at Screening, or past history of Jo-1 Ab positivity.

- 18. Any other condition or circumstance that, in the opinion of the investigator, would be likely to prevent adequate compliance with the study protocol.
- 19. Significant and/or acute illness (eg, change in pulmonary status, infection requiring antibiotics) within 5 days prior to (the first) drug administration that may impact safety assessments, in the opinion of the Investigator.

Test Products, Doses, and Mode of Administration:

ATYR1923 (or matching Placebo) will be provided in vials of 25 mg/mL strength. Placebo infusion will be identical in appearance to the active drug to maintain blinding.

All investigational product will be administered via an IV infusion over a 60-minute duration.

For the preparation of the ATYR1923 dose levels the weight of the patients at Screening will be used.

Duration of Screening, Treatment and Follow-up:

The duration of patient participation is up to 28 weeks, including:

- A Screening period for up to 4 weeks in duration.
- A 20-week treatment period with six (6) study drug infusions administered every 4 weeks.
- An EOS visit, 4 weeks after last study drug infusion.

Note that patients with elevated confirmed positive Jo-1 antibody titers or who have ongoing study drug-related treatment-emergent adverse events (TEAEs) at Week 24/EOS will continue to be followed until resolution or determined by the Investigator to be stable (eg, by telephone contact or unscheduled visit).

Duration of Study:

Approximately 2 years.

Study Endpoints:

Primary:

Safety

Safety and tolerability of multiple IV doses of ATYR1923 in patients with pulmonary sarcoidosis based on the following analyses:

• Incidence of TEAEs and serious adverse events (SAEs).

Secondary:

Potential to Decrease Background Oral Corticosteroid Dose

- Total cumulative steroid dose administered over the primary study period (Day 1 through Week 24).
- Number of patients who achieve the targeted tapered dose of prednisone 5 mg/day (or equivalent) and maintain it through Week 24.

 Exposure response analysis comparing steroid dose area under the curve (AUC) with ATYR1923 PK parameters through Week 24.

Immunogenicity

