3.3. Summary of Statistical Analysis Changes to the Protocol

The PK Concentration Parameter Analysis Set included in the protocol, Section 10.1.1.4, is not included in this SAP. Instead, an Efficacy Evaluable Set has been added. The Intent to Treat (ITT) Analysis Set is included in the Protocol, Section 10.1.1.1. However, due to the possibility of subjects who have been randomized but not dosed, a modified Intent-to-Treat (mITT) population is used in the SAP.

aTyr Pharma, Inc.
Study ATYR1923-C-002 Statistical Analysis Plan
IND#: 133692

FINAL Version 1.0
2021-08-02

The first secondary endpoint specified in the protocol specifies the following.

- Total cumulative steroid dose administered over the primary study period (Day 1 through Week 24) by treatment cohort

During planning of this analysis, it was brought to attention that subjects may be dosed for different periods of time, and visits may occur at different study days for different subjects due to scheduling conflicts. Therefore, a time adjusted AUC will be used to examine OCS use.

In the protocol secondary endpoints below are specified for Week 24 visit.

- Total cumulative steroid dose administered over the primary study period (Day 1 through Week 24) by treatment cohort
- Number of patients who achieve the targeted tapered dose of prednisone 5 mg/day (or equivalent) and maintain it through Week 24 by treatment cohort

In light of the half-life of the investigational product, it was decided that the endpoints will be examined for the end of dosing period instead. The end of dosing period is defined as 30 days after the last dose.

In addition, due to protocol prescribed taper prior to Day 51, an additional period, Day 51 through end of dosing interval, will also be examined, together with Day 1 through end of dosing interval.

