4.2.2. Secondary Endpoints

- 1) Potential to Decrease Background Oral Corticosteroid Dose
 - Time adjusted Area Under the Curve (AUC) of steroid dose administered over the study periods (Day 1 through the end of dosing interval and Day 51 through the end of dosing interval) by treatment cohort
 - Number of patients who achieve the targeted tapered dose of prednisone 5 mg/day (or equivalent) and maintain it through the end of dosing interval by treatment cohort
 - Exposure response analysis comparing steroid dose area under the curve (AUC) with ATYR1923 PK parameters through Week 24. This endpoint is not analyzed based on this analysis plan. A separate document is prepared for all PK related analyses.
- 2) Immunogenicity of multiple IV doses of ATYR1923 in patients with pulmonary sarcoidosis based on the following endpoints:
 - Incidence and titer of positive ADA (anti-ATYR1923) and anti-Jo-1 Ab.

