7.3.3.4. Imputation Methods for Missing OCS Dose Data

OCS dosage levels will not be imputed, and those that are recorded as "ongoing" or are missing an end date in the collected OCS information will be assumed to have been taken up to the date of last visit. The data listings will not show an end date.

aTyr Pharma, Inc.
 Study ATYR1923-C-002 Statistical Analysis Plan
 IND#: 133692

FINAL Version 1.0
 2021-08-02

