10.1. Potential Decrease in Background Oral Corticosteroid Dose

For analyses in this section, the data will be summarized in different ways if there are missing data values for OCS dose. For details see Section 7.3.3.4.

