10.1.4. Study Drug Adjusted OCS Burden

Since a missed dose in study treatment is likely to affect OCS dose, in order to isolate the effect of treatment, the above mentioned OCS dose, change from baseline and percent change from baseline analyses will be repeated, but excluding a window around a missed dose of study treatment, where a window is defined as 30 days after the previous dose and restart on the day of the next administered dose. Active treatment and placebo will be compared in the same way as in time adjusted OCS burden in the previous section.

10.1.5. Achievement of Target Taper Dose of Prednisone 5 mg/day (or Equivalent) and Maintained Through Week 24

The number and percentage of patients who have achieved the following will be summarized.

1. **Ability to Taper:** Taper OCS dose level down to 5mg/day or less at any time and remained for at least 5 consecutive days.
2. **Maintain Taper:**
 - a. Taper OCS dose level down to 5mg/day or less at any time and remained for at least 30 consecutive days.
 - b. Taper OCS dose level down to 5mg/day or less at any time and remained for at least 60 consecutive days.
 - c. Taper OCS dose level down to 5mg/day or less at any time and remained for at least 90 consecutive days.
 - d. Taper OCS dose level down to 5mg/day or less at any time and remained for at least 115 consecutive days

- e. Time to first relapse of taper for sarcoidosis. Defined as the duration from the first day of hitting 5mg (plus 5 consecutive days) to when >5mg is needed. If the reason for increase in OCS is unrelated to sarcoidosis (as identified from the eCRF) then that episode will not count as a relapse and counting of the duration will recommence on the next day on which 5mg is achieved. For patients who maintain 5mg after successful taper will be censored at 30 days after last dose or EOS (if earlier). Patients who never reach 5 mg will be assigned a duration of 1 day and be classified as a censored data point.
- f. Proportion of days at 5mg or less ignoring diary days when OCS dose was increased >5mg for non-sarcoidosis events (i.e. same exclusion as the Time to First Relapse endpoint)
- g. Proportion of days at 5mg or less including all diary days (i.e. even those when OCS dose was increased >5mg for non-sarcoidosis events)

In each of the above endpoints, when study drug dosing is missed, OCS diary data >30 days after previous study drug infusion will be ignored until dosing restarted as described in Section 10.1.4.

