For each of the first 4 taper maintenance endpoints above, 2-sided Fisher's exact test will be performed between each individual active treatment arm and combined placebo, using the pseudo code below.

```
proc freq data = taper (where=(treatment in ("Treatment A", "Placebo")));
  table taper_var*treatment / fisher;
run;
```

For the 5th of the "Maintain taper" endpoints (i.e. Time to first relapse of taper), Kaplan-Meier methods will be used to derive estimates of median (& 95% CI) of the time to first taper relapse. A log-rank test will be performed between each individual/combined active treatment arm and placebo to obtain p-values versus placebo. Kaplan-Meier curve will be presented as well. The following pseudo SAS code is used.

```
proc lifetest;
  time duration*status(0);
  strata treatment / test=logrank;
run;
```

where 0 indicates no relapse.

For 6th and 7th of the "Maintain taper" endpoints (i.e. Proportion of days at 5mg or less) descriptive statistics (Mean, SD etc) will be used to informally compare groups. A Wilcoxon rank sum test will be performed between each individual/combined active treatment arm and placebo to obtain p-values versus placebo. The following pseudo SAS code will be used.

aTyr Pharma, Inc.
Study ATYR1923-C-002 Statistical Analysis Plan
IND#: 133692

FINAL Version 1.0
2021-08-02

```
proc nparlway wilcoxon correct=no;  
  class treatment;  
  var days_at_5mg;  
  exact wilcoxon;  
run;
```

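### SAP 10.1.5 never counts the patients who reach 5 mg/day and hold it to the stated end point; its Fisher-tested items count runs of fixed length wherever they fall

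*SAP*

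**What the plan says.** The protocol synopsis lists this secondary endpoint: "Number of patients who achieve the targeted tapered dose of prednisone 5 mg/day (or equivalent) and maintain it through Week 24". SAP 4.2.2 keeps the count but moves its end: "Number of patients who achieve the targeted tapered dose of prednisone 5 mg/day (or equivalent) and maintain it through the end of dosing interval". SAP 3.3 explains the move by the half-life of the product and fixes the new end: "The end of dosing period is defined as 30 days after the last dose". The heading of SAP 10.1.5 still names Week 24.

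Under that heading SAP 10.1.5 lists:

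- Item 1 (ability to taper): 5 mg/day or less for at least 5 consecutive days.
- Items 2a to 2d (maintain taper): the same dose for at least 30, 60, 90 or 115 consecutive days. All four share one wording; 2d is "Taper OCS dose level down to 5mg/day or less at any time and remained for at least 115 consecutive days".
- Item 2e: time to first sarcoidosis-related relapse. Maintainers are censored at 30 days after the last dose, or at EOS if earlier. For the rest: "Patients who never reach 5 mg will be assigned a duration of 1 day and be classified as a censored data point".
- Items 2f and 2g: proportion of days at 5 mg or less, without and with days of non-sarcoidosis increases.

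On testing: "For each of the first 4 taper maintenance endpoints above, 2-sided Fisher's exact test will be performed", each active arm against combined placebo. Item 2e has a log-rank test, and 2f and 2g have Wilcoxon tests.

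On incomplete data, Protocol 10.1.1.6 leaves the handling of early discontinuers to the SAP. SAP 10.1 says "the data will be summarized in different ways if there are missing data values for OCS dose" and refers to 7.3.3.4. That section does not impute doses, and says that open records "will be assumed to have been taken up to the date of last visit".

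**The concern.** The endpoint is a yes-or-no status at a defined end: did the patient reach 5 mg/day and still hold it there? Items 2a to 2d ask whether the patient ever had a long enough run. A patient can complete a run, return to a higher dose and finish the trial there, yet count as maintained. A patient who reaches the target late, or stops dosing early, can hold to the end and still fail the longer run lengths.

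At stake is whether the study report can give a secondary endpoint named in both documents. With 8 active patients per cohort and 12 pooled placebo patients planned, one reclassified patient moves an arm by 100/8 = 12.5 or 100/12 = 8.3 percentage points. SAP 3.3 lists the departures from the protocol but does not mention this one.

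**Working it through.** **Inputs**

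- Week 24/EOS is Day 169; the fourth and sixth infusions are on Days 85 and 141 (Protocol Table 1).
- End of dosing is last dose + 30 days (SAP 3.3). On the full schedule this is 141 + 30 = Day 171, so Day 169 comes first and is used below. Using Day 171 adds 2 days to every tail.
- The taper starts on Day 15, is due by Day 50, and goes in 5 mg steps every 1 to 2 weeks (Protocol 7.1.6.2). Under those steps a 10 mg starter can reach 5 mg on Day 15. A 25 mg starter on weekly steps goes to 20, 15, 10 and 5 mg on Days 15, 22, 29 and 36.
- Run lengths L are 30, 60, 90 and 115 days (SAP 10.1.5). The documents give no derivation for them and no power calculation, so there is no plan figure to reproduce.

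**Relapse that still counts as maintained**

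A run of L days from Day s ends on Day s + L − 1. The uncovered tail is 169 − (s + L − 1). Holding from Day s through Day 169 takes 169 − s + 1 days. Cells show run end / tail.

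| First day at 5 mg | 2a | 2b | 2c | 2d | Days needed to hold to Day 169 |
|---|---|---|---|---|---|
| 15 | 44 / 125 | 74 / 95 | 104 / 65 | 129 / 40 | 155 |
| 36 | 65 / 104 | 95 / 74 | 125 / 44 | 150 / 19 | 134 |
| 50 | 79 / 90 | 109 / 60 | 139 / 30 | 164 / 5 | 120 |

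In the Day 15 row, a patient who relapses on Day 130 and stays above 5 mg for all 40 days to Day 169 is a responder on all four items.

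Item 2d coincides with holding through Day 169 for one start day only: 169 − 115 + 1 = Day 55. An earlier start leaves a tail; a later one cannot complete the run by Day 169.

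**Maintained but missed by 2d**

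- First at 5 mg on Day 60 and held to Day 169: 169 − 60 + 1 = 110 days, below 115. Neither endpoint wording sets a deadline for reaching 5 mg.
- Last dosed on Day 85: the dosing interval ends on Day 85 + 30 = 115, and 10.1.5 ignores later diary data. The longest run is 115 − 15 + 1 = 101 days. This patient can meet the 4.2.2 endpoint but never 2d.

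**Why 2e to 2g do not supply the count**

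Item 2e censors both maintainers and patients who never reached 5 mg, so the number censored mixes success with failure. It also disregards non-sarcoidosis increases. Items 2f and 2g are shares of days and require neither continuity nor holding to the end.

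**Ignored days**

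The SAP does not say whether diary days dropped after a missed infusion break a run or are bridged. Take infusions on Days 57 and 113 with Day 85 missed. Days 88 to 112 (25 days) are ignored. With 5 mg on Days 50 to 87 (38 days) and 113 to 169 (57 days), the run is 38 + 57 = 95 days if bridged, which meets 2c. If broken, the longest run is 57 days, which fails 2b.

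**The case against.** The strongest reply is that the information is already in the plan. Item 1 identifies achievers and 2e records relapses up to 30 days after the last dose or EOS, so achievers minus relapse events gives something close to the count. This stands in part. A reader might infer that nothing in 10.1.5 is tied to an end point, or that only run lengths are tested. Neither is so: 2e is tied to both ends and has a log-rank test, and 2f and 2g are tested too. But the subtraction is not a planned row, leaves out non-sarcoidosis increases, and treats a diary that stops early as maintained. The data are there; the definition is missing.

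Second, 2d is a fair proxy for a patient who reaches 5 mg around the Day 50 deadline, where the tail is only 5 days. That stands for those patients. It does not carry over to earlier or later achievers, to patients who stop dosing early, or to 2a to 2c.

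Third, a late relapse would show in 2f and 2g, in the time-adjusted AUC from Day 51, and in the individual dose plots of 10.1.6. True, but none of these reports how many patients held.

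**Conclusion.** The point holds: a secondary endpoint named in both documents has no matching analysis in SAP 10.1.5, and the Fisher-tested substitutes can classify patients differently from it in both directions. For 2d the unobserved tail to Day 169 is 40, 19 or 5 days for 5 mg reached on Day 15, 36 or 50; for 2a from Day 50 it is 90 days. In the other direction, 110 days held to Day 169 fails 2d, as does every patient last dosed on Day 85. SAP 3.3 discloses the change of end point but not the replacement by run lengths.

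Two stronger readings are not supported. A reader might infer that a patient with four doses who is at 5 mg on Days 50 to 115 is wrongly counted as maintained under 2a and 2b (115 − 50 + 1 = 66 days). Under 4.2.2 that patient's interval ends on Day 115, so the endpoint is met; only against Week 24 is the patient 169 − 115 = 54 days short. Nor is a confirmatory claim at risk: the primary endpoint is safety, and SAP 7.4.1 and 7.5 make all testing exploratory and unadjusted. The effect is on how the steroid-sparing result is read, so this should be fixed but does not undermine the trial.

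Assumptions: nominal visit days, and taper steps as in Protocol 7.1.6.2, because the separate Taper Guidelines are not among the documents. The number of patients who would be reclassified cannot be known from the plan.

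**What to change.** Add as the first maintenance item of SAP 10.1.5 the number and percentage of patients at 5 mg/day or less from sustained achievement (the 5-day rule of item 1) through the 4.2.2 end point: last dose + 30 days, or EOS if earlier. Give the protocol's Week 24 version as a second row.

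- In both rows, count never-achievers as not maintained.
- Count a patient whose diary stops before that row's end point as not maintained, with an observed-data version as sensitivity. A single fixed cut-off day for both rows should be avoided, because it would impose Week 24 on the 4.2.2 row.
- Apply the Fisher test to this count, and show it with and without non-sarcoidosis increases, as 2f and 2g already do.
- State whether days ignored after a missed infusion break or bridge a run, and whether a patient who re-tapers after rescue and then holds to the end counts.
- Make the 10.1.5 heading match 4.2.2, relabel 2a to 2d as supportive (run length at any time), and list the change in 3.3.

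The cost is SAP wording, flags derived from existing diary data and a few table rows. The reported maintained proportion may be lower than under 2a to 2c.

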10.1.1. OCS Data Sources

The sources of OCS use are summarized in the table below.

Time of Use	Data Source	CRF Name	Comments
Historical and current use at Screening	OCS LOG	OCS Log - Prior and Current Use table	Historical use will be added here. An additional row for every change in steroid or dose
Steroid use beginning on Day 1	eDiary	Patient Diary	Patients will be entering a form every day and from that data we can pull out any dosing changes or changes in use
	OCS LOG (for subjects who do not have eDiary)	OCS Log - Prior and Current Use table	Study Coordinators will be responsible for recording any dosing changes or changes in steroid use in this table based on the paper diaries completed by the subject

aTyr Pharma, Inc.
 Study ATYR1923-C-002 Statistical Analysis Plan
 IND#: 133692

FINAL Version 1.0
 2021-08-02

Changes in Dose	eDiary and OCS LOG for subjects without eDiary	Patient Diary and OCS Log - Prior and Current Use table	
-----------------	--	---	--

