10.1.3. Time adjusted OCS Burden

Time adjusted AUC is a measure of steroid burden and approximates the mean steroid usage post-baseline for each patient. For each patient, it is calculated and summarized as follows,

$$Time\ Adjusted\ AUC = \sum_{t=M}^{N-1} \frac{AUC}{N-M} = \sum_{t=M}^{N-1} \frac{(C_t + C_{t'}) (t' - t)}{2(N-M)},$$

where

C_x is the OCS dose in mg on day x ,

t' is the study day of the next known OCS daily dose after day t ,

M and N are start and end study days of the analysis periods of interest. In this study, we are interested in the time periods a) Day 1 through end of dosing period (30 days after last dose) or day of last known OCS dose (if earlier than end of dosing period) and b) Day 51 through end of dosing period (30 days after last dose) or day of last known OCS dose (if earlier than end of dosing period).

Similarly, change from baseline and percent change from baseline at each diary entry will be used as C_x in the formula above, and analyses will be repeated.

aTyr Pharma, Inc.
Study ATYR1923-C-002 Statistical Analysis Plan
IND#: 133692

FINAL Version 1.0
2021-08-02

In addition, active treatment arm for each cohort and combined active arm are compared to combined placebo using the following pseudo code.

```
proc glm data = auc;  
  class treatment(ref=Placebo);  
  model auc = treatment baselineOCS / solution;  
  lsmeans treatment / pdiff=control("Placebo") adjust=T cl;  
run;
```

The difference between LS means, 95% Confidence Intervals and p-values will be presented.

Time adjusted AUC for Day 1/51 through end of treatment periods will be summarized using density and box plots by treatment.

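### SAP 10.1.5 item 2e (time to first relapse) has no censoring limit at the last known steroid dose, so days without any dose record can count as relapse-free

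*SAP*

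**What the plan says.** SAP 10.1.5 item 2e measures time from first reaching 5 mg to the first sarcoidosis-related dose above 5 mg. For patients without a relapse the rule is: "For patients who maintain 5mg after successful taper will be censored at 30 days after last dose or EOS (if earlier". SAP 3.3 fixes the 30-day horizon: "The end of dosing period is defined as 30 days after the last dose". The analysis follows in the same section: "Kaplan-Meier methods will be used to derive estimates of median", with a log-rank test of each active arm and the combined active arm against placebo.

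Three other places bear on what is observed:

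- **SAP 10.1.1.** From Day 1 the source is the eDiary: "Patients will be entering a form every day and from that data we can pull out any dosing changes or changes in use". Patients without an eDiary have an OCS log filled from paper diaries.
- **SAP 10.1.3.** The time-adjusted AUC ends at the end of the dosing period "or day of last known OCS dose (if earlier than end of dosing period". This is stated for both AUC periods.
- **SAP 7.3.3.4.** "OCS dosage levels will not be imputed", but in the same sentence doses marked as ongoing or lacking an end date "will be assumed to have been taken up to the date of last visit". The opening of SAP 10.1 points to this rule for all the OCS analyses.

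**The concern.** A relapse in item 2e is a recorded dose above 5 mg, so it can be seen only on days with a known dose. The AUC analysis stops where the records stop. Item 2e, built on the same records, does not. A patient whose records end while still at 5 mg stays in the risk set, unable to have an event, until 30 days after the last infusion or EOS.

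Holding such patients at risk adds no events and enlarges the later risk sets. The Kaplan-Meier curve is therefore never lower, and can be higher, than with censoring at the last record. The relapse-free estimate and the reported median are pushed in the favourable direction, in whichever arm records are lost.

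**Working it through.** The documents give no power, event or diary-loss figure for this endpoint, so there is no planned figure to reproduce.

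**Inputs from the documents**
- Last planned infusion Day 141, EOS Day 169 (Protocol Table 1).
- Taper to 5 mg complete by Day 50 (Protocol 4.1).
- 8 active patients per cohort, 24 active in total, 12 pooled placebo (Protocol 4.1 and 5).

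**Assumptions, not in the documents**
- Exponential relapse times, with true relapse-free share S of 30% to 70% at 119 days.
- A share q of diaries, 10% to 40%, ends early, independently of relapse.
- No relapse after the last record is ever seen.

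**Step 1: dates.** With full dosing, censoring is at min(141 + 30, 169) = Day 169. A patient at 5 mg from Day 50 is credited 169 − 50 = 119 days.

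| Last record | Unobserved days | Share of 119 |
|---|---|---|
| Day 141 | 28 | 24% |
| Day 113 | 56 | 47% |
| Day 85 | 84 | 71% |

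A patient lost after an infusion, with no EOS date before the 30 days are up, is credited up to 30 days beyond the last visit. The 7.3.3.4 carry-forward does not cover those days, because it ends at the last visit.

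**Step 2: Kaplan-Meier estimate.** Under item 2e everyone without a recorded relapse is held to day 119, so the estimate there is the share with no recorded relapse:

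(1 − q)·S + q·E[exp(−λU)], with λ = −ln(S)/119 and U the time of the last record for a diary that ends early.

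*Stopping uniform over the 119 days.* E = (1 − S)/(−ln S). For S = 0.5: 0.5/0.6931 = 0.721. With q = 0.2: 0.8 × 0.5 + 0.2 × 0.721 = 0.544.

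*Stopping only within the last 28 days.* E = [exp(−91λ) − exp(−119λ)]/(28λ). For S = 0.5, λ = 0.6931/119 = 0.005825, so E = (0.5886 − 0.5)/0.1631 = 0.543. With q = 0.2: 0.4 + 0.2 × 0.543 = 0.509.

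Uniform stopping over the assumed range:

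| True share | q = 10% | q = 20% | q = 40% |
|---|---|---|---|
| 70% | 71.4% | 72.8% | 75.6% |
| 50% | 52.2% | 54.4% | 58.9% |
| 30% | 32.8% | 35.6% | 41.3% |

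With censoring at the last known dose, the estimate targets the true share in this model.

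**Step 3: log-rank test.** Simulation, 4,000 runs per case, no true treatment effect, S = 30%, uniform stopping:

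| Active v placebo | Diary loss | Measure | Item 2e | Last known dose |
|---|---|---|---|---|
| 24 v 12 | 20% v 20% | two-sided rejection | 5.3% | 5.6% |
| 24 v 12 | 40% v 0% | two-sided rejection | 9.6% | 5.4% |
| 24 v 12 | 40% v 0% | favours active | 9.0% | 3.3% |
| 24 v 12 | 40% v 10% | favours active | 6.8% | 3.6% |
| 8 v 12 | 40% v 0% | favours active | 5.7% | 2.0% |

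Equal loss leaves the error rate essentially unchanged. Sharply unequal loss does not.

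**The case against.** **The rule may not apply to these patients.** It covers patients who maintain 5 mg, and someone whose records stop has not been shown to do so. That reading is possible. The SAP would then have no censoring rule for a diary that stops, and the same sentence would still be needed.

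**Section 7.3.3.4 already fills gaps.** This stands in part. A reader who takes only the no-imputation half of that sentence might infer that item 2e flatly contradicts it. The other half declares a carry-forward to the last visit. Where it applies and EOS is attended, the known dose runs to EOS and the proposed limit changes nothing. It does not clearly cover daily eDiary forms that cease, and it does not reach past the last visit.

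**EOS already caps the time.** Early stoppers are asked to attend EOS (Protocol 6.4.1 and 6.4.2). If EOS also means the end-of-study date of a patient who leaves without that visit, the 30 extra days disappear. Neither reading helps with a patient who keeps attending but stops the diary.

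**Long gaps are unlikely.** Diaries are reviewed at relevant calls and visits (Protocol 7.1.6.2 and 7.1.6.3), and concomitant medication is assessed at every contact (Protocol Table 1). This stands: unseen gaps of many weeks are a worst case, which is why the 28-day figure is shown beside the uniform one.

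**The bias is small against the noise.** The standard error of a 50% share is √(0.25/12) = 14 points with 12 patients and √(0.25/24) = 10 points with 24. This also stands, and it limits the importance of the point.

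**Conclusion.** Wrong as written, with modest impact. Item 2e lacks the limit that SAP 10.1.3 applies to the same data. Any records that end early and fall outside the 7.3.3.4 carry-forward raise the relapse-free estimate. At a true share of 50% and 20% early-ended diaries, the estimate is about 51% if only up to the last 28 days are unseen and about 54% under uniform stopping. Both figures rest on the assumed loss rate, exponential relapse times and stopping unrelated to relapse.

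A reader might infer that the rule manufactures a treatment effect. The documents do not support that: they give no diary-loss rate and no reason to expect different loss by arm in a double-blind trial. The false-positive rate rose clearly only under marked imbalance. A reader might also infer that the added limit cures bias from patients who stop recording as they worsen. It does not, because that censoring is informative under either rule.

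The study has no power calculation (SAP 6), no formal hypothesis testing (SAP 7.4.1) and unadjusted exploratory tests (SAP 7.5). Item 2e is one of several maintenance summaries. The change is still worth making, because the error runs in one direction and is easily removed.

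**What to change.** In item 2e, censor relapse-free patients at the earliest of 30 days after last dose, EOS, and the day of the last known OCS dose, as in SAP 10.1.3. State that a known dose includes one carried to the last visit under 7.3.3.4. Keep the current rule as a sensitivity analysis if wanted.

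SAP 10.1.5 also says that "OCS diary data >30 days after previous study drug infusion will be ignored until dosing restarted". The derivation should state whether days set aside in this way count as known.

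The cost is one phrase and one extra date in the censoring derivation. Some patients will be censored earlier, so intervals widen slightly. Reporting, by arm, how many patients have records ending before the current censoring date would show whether the issue matters in practice and whether stopping may be related to worsening.
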